	
2 OADs which may include metformin at a dose of at least 1500 mg/day or the maximum tolerated dose (documented). Patients who satisfy the entry criteria will be switched to Lantus® (1:1 dose conversion from basal insulin being used at Screening).
 
The trial will consist of 3 periods:
 
• An up to 6-week Screening Period comprised of:
- An up to 2-week Screening phase- A 4-week Lantus titration/single-blind placebo Run-in Phase.• A 52-week double-blind Treatment Period comprised of:
- An initial 18-week fixed-dose phase during which Lantus dose is held constant except for safety reasons- Subsequent 34 weeks during which Lantus can be titrated.• A 2-week, post-treatment Follow-up Period. 
Screening Period
 
Up to 2-week Screening phase (see Section 1.2)
 
4-week Lantus titration/single-blind placebo Run-in Phase
 
If the patient satisfies the entry criteria, their basal insulin will be converted to Lantus supplied by the Sponsor (1:1 conversion based on units) and a 4-week Lantus optimization phase will commence at Week -4 (Visit 2).
 
Lantus titration: The target range of fasting SMBG is 80-100 mg/dL (4.4-5.6 mmol/L). The titration will be based on SMBG readings performed before the first meal of the day for at least 5 days per week. The Lantus dose will be adjusted based on the mean of the 3 most recent fasting SMBG values according to the following titration rule:
 
• ≥ 140 mg/dL (≥ 7.8 mmol/L): increase Lantus by 4 units, or split to 2 x 2 units• ≥ 120 mg/dL (≥ 6.7 mmol/L) but < 140 mg/dL (< 7.8 mmol/L): increase Lantus by 2 units• > 100 mg/dL (> 5.6 mmol/L) but < 120 mg/dL (< 6.7 mmol/L): increase Lantus by 1 unit• 80-100 mg/dL (4.4-5.6 mmol/L), inclusive: no change in dose• < 80 mg/dL (< 4.4 mmol/L): decrease Lantus by 2 units. 
Lantus dose adjustment will occur every 3 days (twice a week). The dose adjustments will be made in consultation with the study site either at site visits, phone visits, or unscheduled phone contacts. In case of hypoglycemia, insulin titration may be withheld according to the Investigator's medical judgment.
 
During the 4-week Lantus titration/single-blind placebo Run-in Phase, patients will also take single-blind placebo, given as two (2) placebo tablets (identical to sotagliflozin 200 mg in appearance), once daily before the first meal of the day. In order to qualify for randomization, patients must demonstrate compliance at the end of

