
Noninvestigational medicinal product(s)
	
Placebo
 
 • Tablets identical in appearance to sotagliflozin 200 mg • Oral • Two (2) placebo tablets, once daily before the first meal of the day. 
Lantus (insulin glargine, 100 U/mL)
 
 • Prefilled pen (3.0 mL solution) • Subcutaneous injection • Lantus to be provided by the Sponsor at the beginning of the Lantus titration phase. Patients who are receiving any basal insulin other than Lantus before screening will switch to Lantus. For patients who are using long-acting insulin analogs other than Lantus (eg, Levemir, Tresiba, Basaglar), the existing basal insulin will be converted to an equivalent dose of Lantus on a 1:1 unit basis (ie, the same dose on the day before Visit 2). If the patient is using Toujeo® (glargine U-300/mL), the initial Lantus dose is 80% of the existing Toujeo dose as recommended in the Lantus label. If the patient is using NPH twice daily, it's recommended that the converted Lantus dose should be reduced by 20% and given once daily. If using NPH once a day, it can be converted to Lantus unit-to-unit. • Metformin (optional) tablets to be administered as per Principal Investigator and in accordance with local labeling • Other OADs (up to 2 in total, including metformin) to be administered as per Principal Investigator and in accordance with local labeling, with the exception of SGLT2 inhibitors.
	
Rescue Therapy
 
The threshold values for rescue are defined as follows, depending on study period:
 
 • From Baseline Visit (Visit 6, Day 1) to Visit 10 (Week 8) (including value at Visit 10): FPG >270 mg/dL (15.0 mmol/L) • From Visit 10 (Week 8) to Visit 11 (Week 12) (including value at Visit 11): FPG >240 mg/dL (13.3 mmol/L) • From Visit 11 (Week 12) up to Visit 12 (Week 18): FPG >200 mg/dL (11.1 mmol/L) or HbA1c ≥8.5% (the 8.5% criteria does not apply if the HbA1c decrease from Baseline was ≥1.5%) • From Visit 12 (Week 18) up to the EOT, Visit 15 (Week 52): FPG >170 mg/dL (9.4 mmol/L) or HbA1c ≥8.0% (the 8.0% criteria does not apply if the HbA1c decrease from Baseline was ≥1.5%). 
Routine fasting SMBG and central laboratory alerts on FPG (and HbA1c at Week 12 and onwards) are set up to ensure that glycemic parameter results remain within predefined thresholds.

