4.4 RATIONALE FOR STUDY DESIGN AND CONTROL GROUPS

This study is designed to assess the efficacy and safety of sotagliflozin (compared to placebo) when used as add-on therapy to basal insulin (Lantus), alone or in combination with oral antidiabetes drugs (OADs). Patients will be switched from their current basal insulin to Lantus (1:1 dose conversion, or 20% reduction if on treatment with Toujeo or Neutral Protamine Hagedorn [NPH] twice daily) and will have a 4-week dose titration period to improve their basal insulin dose prior to Randomization, utilizing a standard titration algorithm. During this period, compliance with the algorithm will be reviewed by an internal group blinded to the treatment assignment and investigators will be contacted as needed to encourage adherence to titration algorithm. During this Lantus titration period, the dose of concomitant OADs should stay unchanged, except if decreases are needed due to hypoglycemia.

The primary endpoint is HbA1c reduction from Baseline to Week 18 because it is expected that sotagliflozin can provide significant additional glycemic efficacy even in an advanced T2D population with presumed beta cell failure. During the first 18 weeks no adjustment of Lantus is permitted (except for safety reasons or if rescue criteria are met) to enable the assessment of the effect of randomized treatment drug on top of a stable background therapy of insulin \pm OADs. After Week 18, titration of Lantus may resume following the same titration algorithm utilized during the Run-in period. This will enable the assessment of the effect of the randomized study drug in a context of total dose of insulin being simultaneously adjusted and more typical of a real-world setting. Prandial insulin or GLP-1 agonists will be the recommended rescue therapy for patients on a stable regimen of oral antihyperglycemic agents who cannot adequately achieve glycemic control by up-titrating their Lantus dose, as per international diabetes treatment guidelines (13, 14). However, the investigator will be allowed to choose from any antidiabetic agent (with the exception of the SGLT2 inhibitors class) according to their clinical judgment and in line with the local standard of care. The protocol stipulates that patients be provided rescue therapy according to increasingly stringent hyperglycemia criteria (based on FPG and/or HbA1c) as aligned with regulatory guidance (15).

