8.2.1.2 Starting dose

From Visit 2 (start of the single-blind Run-in period) all patients will receive Lantus as basal insulin. Patients who are already receiving Lantus prior to the study will start Run-in (Visit 2) at their pre-study dose level.

Patients who are receiving any basal insulin other than Lantus before Screening will switch to Lantus once a day. For patients who are using long-acting insulin analogs other than Lantus (eg, Levemir, Tresiba, Basaglar) the existing basal insulin will be converted to an equivalent dose of Lantus on a 1:1 unit basis (ie, the same dose on the day before Visit 2). If the patient is using Toujeo (glargine U-300/mL), the initial Lantus dose is 80% of the existing Toujeo dose as recommended in the Lantus label. If the patient is using NPH twice daily, it's recommended that the converted Lantus dose should be reduced by 20% and given once daily. (If using NPH once a day, it can be converted to Lantus unit-to-unit.)

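### The synopsis design text twice gives an unqualified 1:1 conversion to Lantus, which contradicts the 20% lower starting dose given elsewhere for prior Toujeo and twice-daily NPH

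*Protocol*

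**What the plan says.** **Clinical Trial Summary, Study Design.** The switch to Lantus appears twice. The first statement covers all patients who satisfy the entry criteria: "1:1 dose conversion from basal insulin being used at Screening". The second, under the run-in heading, says that the basal insulin will be "converted to Lantus supplied by the Sponsor (1:1 conversion based on units"). Neither sentence names an exception or refers to the treatment section.

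**Clinical Trial Summary, treatment row for Lantus, and Section 8.2.1.2 (Starting dose).** Long-acting analogs other than Lantus convert 1:1, and once-daily NPH converts unit-to-unit. Toujeo is an exception: "the initial Lantus dose is 80% of the existing Toujeo dose as recommended in the Lantus label". Twice-daily NPH is the other: "If the patient is using NPH twice daily, it's recommended that the converted Lantus dose should be reduced by 20% and given once daily".

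**Section 4.4.** The rationale gives the rule and its exceptions in one clause: "1:1 dose conversion, or 20% reduction if on treatment with Toujeo or Neutral Protamine Hagedorn [NPH] twice daily".

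**Sections 6.1.1.2 and 8.2.1.** Section 6.1.1.2, the body's counterpart of the synopsis run-in text, gives no ratio and refers to Section 8.2.1. Section 8.2.1 sends the reader on to 8.2.1.2, among other sections, for dosing.

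**Section 7.1.** Inclusion criterion I 01 admits patients on any type of basal insulin, so both excepted groups can enter.

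**The concern.** The instruction at issue is the first dose of study-supplied insulin. Read as written, the two Study Design sentences apply to every eligible patient, including those coming from Toujeo or twice-daily NPH. Three other places give those patients a lower start. Section 4.4 shows that the exception fits into a short statement of the rule, so brevity does not explain its absence from the design text.

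The Visit 2 procedure list (Section 10.1.1.2.1), which a site would follow on the day, has Lantus dispensed and started but gives neither a conversion nor a pointer to 8.2.1.2. If sites take the rule from different places, patients with the same prior insulin could begin the run-in on different doses. Hypoglycemia risk in the first days of the run-in could then differ between sites. The affected groups were expected: SAP Section 2.1.1 tabulates prior basal insulin with separate categories for glargine 300 U/mL and NPH.

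**Working it through.** **1. The stated exceptions agree with one another.** Section 4.4 gives a 20% reduction, and 1 − 0.20 = 0.80. That matches the 80% figure for Toujeo in the treatment row and in 8.2.1.2. For twice-daily NPH, all three places give a 20% reduction.

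**2. The passages side by side.**

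| Prior insulin | Study Design text | Treatment row, 4.4 and 8.2.1.2 | Conflict |
|---|---|---|---|
| Other long-acting analogs | 1:1 | 1:1 | No |
| NPH once daily | 1:1 | 1:1 | No |
| Toujeo | 1:1 | 0.80 × prior dose | Yes |
| NPH twice daily | 1:1 | 0.80 × prior dose (recommended, in the treatment row and 8.2.1.2) | Yes |

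Section 4.4 has no separate entry for once-daily NPH; its general 1:1 rule covers it.

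**3. Size of the conflict.** Ratio = (1.00 × dose) / (0.80 × dose) = 1/0.80 = 1.25 at any prior dose. Seen from the other side, the reduced dose is 20% below the 1:1 dose. The documents give no distribution of prior doses, so the following values are assumed for illustration:

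- 20 units: 20 v 16, difference 4
- 40 units: 40 v 32, difference 8
- 60 units: 60 v 48, difference 12
- 80 units: 80 v 64, difference 16

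**4. How fast the titration rule could close the gap.** Table 2 allows 2 units down or up to 4 units up per adjustment, and run-in adjustments are made every 3 days. For the 40-unit example, the 8-unit gap is 8/2 = 4 downward steps (about 4 × 3 = 12 days) or 8/4 = 2 upward steps at the largest increment (about 6 days), within a 28-day run-in. This is the written pace of the rule and does not predict what happens to a patient. Investigators may withhold titration or reduce the dose sooner.

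**5. Effect on the sample size.** The inputs in Section 11.1 are the SD (1.2%), the differences (0.5% and 0.4%), the two-sided 5% level and the arm sizes (280, 140, 140). The Lantus starting dose is not among them.

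**The case against.** The strongest reply is that the operative text is complete. Apart from Section 4.4, which carries the exceptions, the protocol body gives no summary ratio for the switch. Section 6.1.1.2 leads to 8.2.1, which leads to 8.2.1.2, where the full rule stands under the heading Starting dose. The treatment row of the same synopsis has both exceptions as well. On this view the Study Design text states the general rule and the other places add the exceptions. Most of this stands. It makes a wrong start less likely, but two unqualified sentences about a dose still conflict with three other places.

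Four stronger readings are tempting, and the documents do not support them:

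- **That sites would start these patients 25% too high.** This requires relying on the design row and missing the treatment row, 4.4 and 8.2.1.2. It is a possible reading, not the expected result, and nothing here decides which conversion is right.
- **That all NPH users are affected.** The exception covers twice-daily use only, and in the treatment row and 8.2.1.2 it is a recommendation. Only the Toujeo figure is stated directly.
- **That the uniformity of the titrated background, or the treatment comparison, is compromised.** Four weeks of titration to a fasting target of 80-100 mg/dL follow the conversion, and randomization comes after that. Any remaining difference is not tied to treatment arm, and no effect on background uniformity has been shown.
- **That the passages use conflicting reference dates.** The design text mentions the insulin used at Screening, while the treatment row and 8.2.1.2 refer to the day before Visit 2 for the other analogs. The first can be read as naming the product being replaced rather than dating the dose, so the texts can be compatible.

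**Conclusion.** The contradiction is real and narrow. Two sentences in the synopsis Study Design text give 1:1 for everyone, while the synopsis treatment row, Section 4.4 and Section 8.2.1.2 give a 20% lower start after Toujeo or twice-daily NPH. A site that took its instruction from the design row alone could use a starting dose 1.25 times that in 8.2.1.2.

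The factor of 1.25 follows from the stated percentages. The unit differences above rest on assumed prior doses, and the number of patients affected cannot be derived from the documents. The consequence is limited to consistency of the Visit 2 starting dose and hypoglycemia risk early in the run-in. Treatment comparison, power and planned analyses are unaffected. This is a minor inconsistency, but it deserves correction because it concerns an insulin dose instruction.

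**What to change.** The sponsor should reconcile the two Study Design sentences with the synopsis treatment row, Section 4.4 and Section 8.2.1.2, state which text applies to patients coming from Toujeo and from twice-daily NPH, and add a cross-reference to Section 8.2.1.2 in both sentences. The same edit can make clear which day's dose is converted.

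The cost is a short protocol clarification or a memo to sites. The SAP, the sample size and the data collection need no change.

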1 FLOW CHARTS

1.1 GRAPHICAL STUDY DESIGN

Abbreviations: CGM = continuous glucose monitoring; HbA1c = hemoglobin A1c; MMTT = mixed-meal tolerance test; R = Randomization; T2D = type 2 diabetes.

1.2 STUDY FLOW CHART

	Screening Period					Double-Blind Treatment Period ^a										FU Period
	Screening	Run-in (Lantus titration, single-blind placebo Run-in)				No titration of Lantus (except for safety)						Lantus titration permitted				
VISIT	1	2	3 ^b	4 ^b	5	6	7 ^b	8	9 ^b	10	11	12	13	14	15	16 ^c
Week	-6	-4	-3	-2	-1	0	2	4	6	8	12	18	26	39	52	54
Day (window [days])	-42	-28 (±3)	-21 (±2)	-14 (±2)	-7 (±2)	1 (-)	14 (±3)	28 (±3)	42 (±3)	56 (±3)	84 (±3)	126 (±3)	182 (±3)	273 (±7)	364 (±7)	378 (±3)
Informed consent	X															
Inclusion criteria	X															
Exclusion criteria	X	X	X	X	X	X										
Demographics	X															
Medical/Surgical History	X															
Medication History	X															
Body weight, height ^d	X	X			X	X		X		X	X	X	X	X	X	X
Vital signs ^e	X	X			X	X		X		X	X	X	X	X	X	X
Physical Examination:																
Complete	X												X			
Abbreviated ^f		X			X	X		X		X	X	X		X	X	X
Concomitant Medication	X	X			X	X		X		X	X	X	X	X	X	X
Diet & exercise instruction		X			X	X							X		X	
Instruction on basic GU hygiene & hydration					X	X		X		X	X	X	X	X	X	
Interactive response technology (IRT) contact	X	X				X		X		X	X	X	X	X	X	X

	Screening Period					Double-Blind Treatment Period ^a										FU Period
	Screening	Run-in (Lantus titration, single-blind placebo Run-in)				No titration of Lantus (except for safety)						Lantus titration permitted				
VISIT	1	2	3 ^b	4 ^b	5	6	7 ^b	8	9 ^b	10	11	12	13	14	15	16 ^c
Week	-6	-4	-3	-2	-1	0	2	4	6	8	12	18	26	39	52	54
Day (window [days])	-42	-28 (±3)	-21 (±2)	-14 (±2)	-7 (±2)	1 (-)	14 (±3)	28 (±3)	42 (±3)	56 (±3)	84 (±3)	126 (±3)	182 (±3)	273 (±7)	364 (±7)	378 (±3)
Randomization						X										
Dispense glucose meter, Beta-hydroxybutyrate (BHB) meter		X														
Dispense glucose test strips and BHB strips		X				X	X	X		X	X	X	X	X	X	
Measurement of capillary BHB at the site						X	X	X		X	X	X	X	X	X	
Dispense diary	X	X				X	X	X		X	X	X	X	X	X	
Collect/review diary		X			X	X	X	X		X	X	X	X	X	X	X
Instruction on diabetic ketoacidosis symptoms, glucose testing		X			X	X	X	X		X	X	X	X	X	X	
Dispense IMP and Lantus		X				X	X	X		X	X	X	X	X	X	
IMP and Lantus accounting & compliance					X	X	X	X		X	X	X	X	X	X	
Review results of SMBG and recommend Lantus dose adjustments as necessary ^g		X	X	X	X	X	X	X	X	X	X	X	X	X	X	X
Record results of a 7-point SMBG ^h						X						X			X	
12-lead ECG ⁱ	X					X							X			

	Screening Period					Double-Blind Treatment Period ^a											FU Period
	Screening	Run-in (Lantus titration, single-blind placebo Run-in)				No titration of Lantus (except for safety)							Lantus titration permitted				
VISIT	1	2	3 ^b	4 ^b	5	6	7 ^b	8	9 ^b	10	11	12	13	14	15	16 ^c	
Week	-6	-4	-3	-2	-1	0	2	4	6	8	12	18	26	39	52	54	
Day (window [days])	-42	-28 (±3)	-21 (±2)	-14 (±2)	-7 (±2)	1 (-)	14 (±3)	28 (±3)	42 (±3)	56 (±3)	84 (±3)	126 (±3)	182 (±3)	273 (±7)	364 (±7)	378 (±3)	
Laboratory Assessments ^j																	
FPG ^k	X					X		X		X	X	X	X	X	X		
BHB						X		X		X		X	X	X	X		
HbA1c	X				X	X		X		X	X	X	X	X	X		
Clinical Chemistry ^l	X				X	X		X		X	X	X	X	X	X	X	
Hematology	X					X					X		X	X	X		
Fasting lipids						X						X			X		
Pregnancy test (WOCBP) ^m	X					X		X		X	X	X	X	X	X		
FSH and/or estradiol as needed ^m	X																
Plasma concentration ⁿ								X				X	X		X		
Markers of calcium metabolism ^o						X							X				
Urinalysis w/microscopy ^p	X					X							X				
Collection of home overnight urine for albumin, protein, creatinine, calcium, phosphorus, magnesium, glucose, and albumin-creatinine ratio ^q						X					X		X		X		

	Screening Period					Double-Blind Treatment Period ^a										FU Period
	Screening	Run-in (Lantus titration, single-blind placebo Run-in)				No titration of Lantus (except for safety)						Lantus titration permitted				
VISIT	1	2	3 ^b	4 ^b	5	6	7 ^b	8	9 ^b	10	11	12	13	14	15	16 ^c
Week	-6	-4	-3	-2	-1	0	2	4	6	8	12	18	26	39	52	54
Day (window [days])	-42	-28 (±3)	-21 (±2)	-14 (±2)	-7 (±2)	1 (-)	14 (±3)	28 (±3)	42 (±3)	56 (±3)	84 (±3)	126 (±3)	182 (±3)	273 (±7)	364 (±7)	378 (±3)
PRO: PQAT ^t												X			X	
PRO: TRIM-D ^f	X					X						X	X	X	X	
Evaluate for glycemic rescue	To be assessed and reported throughout the Treatment Period															
Hypoglycemia	To be assessed and reported throughout the study															
AEs/SAEs/AESI/EOSI ^u	To be assessed and reported throughout the study															

- a If a patient discontinues treatment with IMP early during the Treatment Period, the patient will have a Premature EOT Visit, and a Follow-up Visit 2 weeks after the last dose of IMP. However, every effort will be made to have the patients return to the site for all scheduled visits, in particular the visits at Week 18 (Visit 12) and Week 52 (Visit 15). If the patient does not agree to a site visits, the patient will be contacted by telephone to inquire about safety status. If a patient discontinues (or completes) treatment and study at the same time, a single visit for both EOT and EOS will be performed.
- b To ensure effective Lantus dose titration during the Run-in Phase, patients will be instructed to call the Investigator to discuss the necessary adjustments in Lantus dose if they have 2 or more SMBG measurements above 100 mg/dL or below 80 mg/dL.
- c Two weeks after the last dose of IMP.
- d Height to be measured only at Screening.
- e Vital sign measurements (sitting blood pressure [BP], heart rate): 3 separate seated BP and heart rate measurements should be taken with at least 1 minute between readings, following a 5-minute rest period and prior to phlebotomy (if applicable).
- f The abbreviated physical exam should focus on cardiac and respiratory systems, as well as any areas important for assessment of AEs if necessary.
- g Fasting (pre-breakfast/pre-injection if available) SMBG: during the 4-week Run-in Lantus titration period, fasting SMBG should be performed daily. Thereafter, the number of fasting SMBG checks can be reduced according to the Investigator's judgment, however at least 3 fasting (pre-breakfast) SMBG measurements per week should be done from Weeks 0 to 18 and 3 measurements during the week prior to study visits from Weeks 19 to 52 (Section 8.2.1.4). Patients will review SMBG values with site staff either at site visits, phone visits or extemporaneously if patient feels high or low SMBG values may necessitate a dose adjustment. See Table 2 for permitted adjustments. Patients should be advised to check SMBG whenever they experience any symptoms of hypoglycemia, if possible, before taking the treatment. **Note:** Units in table represent plasma glucose values as glucometers used for SMBG display results already adjusted to plasma concentration and no conversion is required.
- h 7-point SMBG profile (before [pre-injection after randomization] and 2 hours after breakfast, lunch and dinner, and bedtime): at least ONE day during the weeks prior to Weeks 0 (Visit 6), 18 (Visit 12), and 52 (Visit 15).
- i The 12-lead ECG recordings should be obtained after at least 10 minutes in a supine position and prior to IMP administration. The ECG will be evaluated as "normal" or "abnormal".

- j* All laboratory assessments occur prior to dose of double-blind IMP (when applicable).
- k* FPG is performed in fasting state, ie, without any food intake (except for water) for at least 8 hours.
- l* Clinical chemistry includes amylase and lipase: please see the list in [Table 4](#).
- m* Serum pregnancy testing only at Screening; urine pregnancy testing subsequently. Serum pregnancy test results must be reviewed prior to beginning the Run-in Phase for all women of childbearing potential (WOCBP, [Appendix A](#)). Any positive urine test results must be confirmed based on serum pregnancy test. The Investigator may perform additional tests at their discretion or as required by local regulations. For women of non-reproductive potentials ([Appendix A](#)), follicle-stimulating hormone [FSH] and/or estradiol levels should be tested in case the definition of postmenopausal or premenopausal can't be satisfied, eg, no medical documents of hysterectomy or cessation of menses without an alternative medical cause is < 12 months.
- n* Plasma concentration samples for sotagliflozin and sotagliflozin-3-O-glucuronide collected on Weeks 4, 18, 26, and 52 may be drawn with the other laboratory assessments but MUST be collected before administration of IMP.
- o* All patients will have lab assessments for markers of calcium metabolism. The markers of calcium metabolism include: serum calcium, serum 25-hydroxyvitamin D, serum 1,25-dihydroxyvitamin D, serum phosphorus, and serum parathyroid hormone.
- p* Urinalysis includes urine dipstick and microscopy. Dipstick includes assessment of specific gravity, pH, protein, blood, ketones, bilirubin, urobilinogen, nitrate, and leukocyte esterase. Microscopy includes, but is not limited to, detection of formed cellular elements, casts, bacteria, yeast, parasites, and crystals in centrifuged urine sediment. In the event of abnormal urinalysis findings suspicious of urinary tract infection (UTI), urine culture should be performed. Positive urine culture determination will be based upon the criteria of the reporting laboratory. Additionally, urine culture should be performed if at any point the Principal Investigator suspects the presence of a UTI.
- q* Patients will collect overnight urine on Weeks 0, 12, 26 and 52 (Visits 6, 11, 13 and 15). In the night prior to the visits: the urine before sleep will be discarded and the urine during sleep and the first morning urine (after getting up) will be collected. The visits should be re-scheduled to allow for the urine collection in case a patient missed it. Urinary albumin, total protein, creatinine, calcium (adjusted for creatinine), phosphorus (adjusted for serum phosphorus and creatinine), magnesium (adjusted for serum magnesium and urinary creatinine) and glucose will be assessed.
- r* [REDACTED]
- t* Patient Reported Outcomes (PROs): Patient Qualitative Assessment of Treatment (PQAT) to be administered to approximately 70 English-speaking patients at Week 18 and 52; Treatment Related Impact Measure - Diabetes (TRIM-D) to be administered to all patients included in the study at Screening, Baseline, and Weeks 18, 26, 39, and 52.
- u* All serious adverse events (SAEs), adverse events (AEs), AEs of special interest (AESI), and events of special interest (EOSI) will be collected starting from signing informed consent and continue until the end of the study. All AEs that occur during treatment should be followed until study completion (or until patients leave the study) or until the event has resolved, the condition has stabilized or the patient is lost to follow-up. All patients will have a Follow-up visit 2 weeks after the last dose of IMP to collect safety information.

